## 2.2 MISSING DATA HANDLING RULE

The primary analysis will be based on the multiple imputation approach for all primary endpoints. [REDACTED]

[REDACTED]

[REDACTED]

[REDACTED]

[REDACTED]

The observed case data (i.e., no imputation for missing values) will be used to supplement the inspection of the impact of missing data on the primary endpoints. [REDACTED]

---

■ [REDACTED]

■ [REDACTED]

■ [REDACTED]

A large number of horizontal black bars of varying lengths, likely representing redacted text or data. The bars are arranged in a grid-like pattern, with some bars being significantly longer than others, creating a visual texture of obscured information.

## 2.3 VISIT WINDOWS

All subjects will undergo a minimum of 11 visits: Preoperative for both eyes; 1st eye operative; postoperative for 1st eye at 8 hours, 1 day, 1 week; 2nd eye operative; postoperative for 2nd eye at 8 hours, 1 day, and 1 week; postoperative for either each eye individually or both eyes together at 1 month and 3 months (depending on gap between surgery of 1st and 2nd eye). The exact number of days allowed for each interval is described in the protocol. The number of eyes with missing visits or data outside of the visit interval will be reported.

## 2.4 DATA CONVENTIONS

For visual acuity data, Snellen acuity will be converted to LogMAR prior to analysis. Formulas used for visual acuity analysis are included in Appendix II. For refractive data, all values will be converted to plus cylinder with sphere adjusted for infinity. Formulas used for refractive data are also included in Appendix II.

## 2.5 TYPE I ERROR RATE

The overall study Type I error rate is 0.025 one-sided. No multiplicity adjustment is necessary for testing non-inferiority of the 2 primary endpoints (1 safety and 1 effectiveness) since both endpoints are required to meet statistical significance. No additional multiplicity adjustment is planned for other effectiveness or safety endpoints.

# 3 ACCOUNTABILITY/ENROLLMENT

Descriptive statistics will typically include sample size (N), mean, standard deviation (SD), median, minimum (Min.), and maximum (Max.) as appropriate for continuous variables. For categorical data, the counts and proportions will be computed.

## 3.1 ACCOUNTABILITY

All summaries will be by OVD and total overall. The number of enrolled subjects will be tabulated by site. Subject accountability will be summarized as a frequency distribution by scheduled visits. A frequency table will be generated, showing the number of available eyes (those in interval and outside of the interval) and the number of missing and active subjects.

 Holladay, J.T., Visual Acuity Measurements, J. Cataract Refract. Surg. Vol 30, Feb, 2004.

## 4 DEMOGRAPHICS AND PREOPERATIVE/OPERATIVE PARAMETERS

Subject level parameters such as demographic variables will be reported by subject. Eye level parameters such as monocular preoperative and/or operative variables will be reported by OVD. For comparison between the OVDs, two-sided alpha of 0.05 will be used. As demographic variables analysis is only exploratory in nature and related to baseline and demographic characteristics to show adequate balance between OVD groups induced by randomization, there will be no multiplicity adjustment. For continuous variables, statistical tests assuming normality will generally be used. However, the data will be reviewed to evaluate whether the normality assumption is appropriate. If it is found not to be appropriate, either an appropriate transformation of the data (i.e., logarithmic) may be used or the corresponding non-parametric tests may be used. Deviations from the proposed statistical guidelines will be substantiated by sound statistical rationale. In this study, unless otherwise indicated, paired t-tests will be used for continuous data, Wilcoxon signed-rank test for ordinal data and McNemar's test for dichotomous data.

Subject demographic data including age, sex, race, ethnicity, and iris color will be presented. Age will be determined at the time of the preoperative visit and will be categorized by less than 60, 60 to 69, 70 to 79, and equal to or older than 80 years old. In addition, continuous age will be summarized with descriptive statistics. The frequency distributions of sex, race, and iris color will also be tabulated. Baseline demographic data will also be reported by site.

Please see Appendix I for list of preoperative and operative parameters to be analyzed.

## 5 POSTOPERATIVE ANALYSES – PRIMARY ENDPOINTS

The safety population will be the primary analysis set for the primary safety endpoint; the mITT population will be the primary analysis set for the primary effectiveness endpoint.

### 5.1 PRIMARY SAFETY ENDPOINT

An IOP spike is defined as an IOP of 30 mmHg or greater. The cumulative rate of IOP spikes (count and proportion of eyes with an IOP spike) at 3 months will be reported by

OVD groups. An eye with an IOP spike is an eye which experienced one or more IOP spikes during the postoperative 3-month follow-up.

[figure not shown]
#### Hypothesis Testing

[figure not shown]
The null and alternative hypotheses for testing the non-inferiority of the test Healon EndoCoat PRO OVD compared to the control Healon EndoCoat OVD with respect to cumulative IOP spike rate at 3 months ( $p$ ) are as follows:

$$H_0: p_{test-control} \geq \delta$$
$$H_A: p_{test-control} < \delta$$

Success Criteria: the upper bound of the 2-sided 95% confidence interval (CI) for  $p_{test-control}$  is less than 10%.

## 5.2 PRIMARY EFFECTIVENESS ENDPOINT

The percent change in ECC from preoperative to 3 months postoperative will be reported by descriptive statistics by OVD groups. The percent change in ECC from preoperative to postoperative is calculated as followed:

[figure not shown]
Percent change in ECC = (Postop ECC minus Preop ECC)/Preop ECC \*100%

### Hypothesis Testing

The null and alternative hypotheses for testing the non-inferiority of the test Healon EndoCoat PRO OVD compared to the control Healon EndoCoat OVD with respect to percent change in ECC at 3 months ( $\mu$ ) are as follows:

$$H_0: \mu_{test-control} \leq \delta$$
$$H_A: \mu_{test-control} > \delta$$

Success Criteria: the lower bound of the 2-sided 95% confidence interval (CI) for  $\mu_{test-control}$  is greater than -5%.

### 5.3 SITE HETEROGENEITY AND OTHER COVARIATES

The analysis of site heterogeneity and of the impact of key covariates on the primary endpoints will be performed using the safety population observed case data for the primary safety endpoint and using the mITT population observed case data for the primary effectiveness endpoint.

When a model approach will be used, any interaction term will be tested at 0.15 significance level.

This figure consists of a grid of horizontal black bars. The bars are of varying lengths, with some being very long and others very short. They are arranged in a grid-like pattern with some vertical spacing. There are also a few small black squares and a vertical line segment on the left side of the grid.

[figure not shown]
## 6 POSTOPERATIVE ANALYSES – OTHER ENDPOINTS

The safety population will be used for the analyses of all other endpoints.

### 6.1 OTHER IOP RELATED ENDPOINTS

The percentage of IOP spikes at 8 hours, 1 day, 1 week, 1 month and 3 months postoperatively will be summarized by OVD and the corresponding 95% CI of the paired-eye difference in proportions will be presented using same method as primary safety endpoint described above. No adjustment in the confidence level for multiple CIs will be made. The count and percentage of IOP spike for the 8-hour visit will also be stratified in 2-hour intervals (6-8 hour and 8-10 hour).

The continuous IOP value and change in IOP from preoperative will be presented by descriptive statistics for the 8-hour (separated by measurements done at 6-8 hours and 8-10 hours), 1-day, 1-week, 1-month and 3-month postoperative time points by OVD. The 8-hour visit will also be stratified in 2-hour intervals (6-8 hour and 8-10 hour).

### 6.2 OTHER ECC RELATED ENDPOINTS

ECC values at preoperative and 3 months postoperative visits, and within-eye change between preoperative and 3 months postoperative visit will be summarized using descriptive statistics.

Count and percent of eyes at 3-month that show % ECC losses from preoperative levels of  $\geq 0\%$ ,  $\geq 10\%$ ,  $\geq 20\%$  to 100%, for every 10% interval will be tabulated.

### 6.3 DISTRIBUTION AND GRADE OF INFLAMMATION

Term	Percentage (%)
GDP	95
Inflation	95
Interest rates	95
Central bank	95
Monetary policy	95
Quantitative easing	95
Inflation targeting	95
Interest rate hike	95
Interest rate cut	95
Interest rate parity	5
Nominal interest rate	5
Real interest rate	5
Nominal GDP	5
Real GDP	5
Nominal exchange rate	5
Real exchange rate	5
Nominal income	5
Real income	5

## 6.4 SERIOUS OR DEVICE-RELATED ADVERSE EVENTS

All SPE types of adverse events reported in the test OVD will be compared to ISO SPE rates using a one-sided 95% Clopper Pearson exact confidence interval. The test AE rate is considered not significantly higher than ISO SPE rate if the lower limit of one-sided 95% confidence interval is less than the SPE rate.

## 6.5 MEDICAL FINDINGS/ADVERSE EVENTS (NON-SERIOUS, NON-DEVICE RELATED)

Rates of medical findings/adverse events will be tabulated with count and proportion of eyes with these events reported over time by OVD.

Reporting of cumulative complications and cumulative adverse events (occurring at any time postoperative either at standard visits) will include data from all study eyes implanted.

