10.9 EXIT OF SUBJECTS

An Exit Case Report Form will be completed for all subjects, either when they complete the study or if they exit early.

It is the responsibility of the investigator to provide complete follow-up data to JJSV for each subject, and every attempt should be made to gather that complete follow-up data for all subjects enrolled as missing data can have a negative effect on the study results. Patients who would be traveling, relocating or otherwise unavailable for postoperative follow-up visits should not be chosen for this clinical study.

Subjects will be discontinued/early terminated from the study if the subject dies, or if the subject is irretrievably lost for unavoidable reasons such as: subject moved/unable to locate, subject uncooperative/refuses further study participation, subject ill/unable to travel. Documentation of efforts to trace subjects that are lost to follow-up and possible reasons are required. In the event of subject relocation, efforts must be made by the

investigator to secure follow-up information (i.e., slit-lamp findings and general visual acuity, etc.) from the subject's new physician.

A subject will be considered a non-randomized screen failure if he/she does not meet the inclusion/exclusion criteria, if consent is withdrawn prior to randomization or death occurs prior to treatment.

A subject will be considered a randomized screen failure if the subject is randomized but does not undergo surgery or does not receive a study/control OVD for various reasons including: subject does not meet the inclusion/exclusion criteria, the planned implant was aborted due to surgical complications, the subject withdrew consent prior to treatment or the subject died prior to treatment. If a subject receives the study or control OVD in at least one eye, he/she is to be followed according to the protocol.

If a subject is exited early from the study, the investigator will complete an Exit Case Report Form in EDC indicating the reason for study exit. In the event of a lens removal or other serious adverse event, the subject may be exited from the study; however, efforts must be made by the investigator to follow the subject until resolution of the adverse event.

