10.10 UNSCHEDULED VISITS

During the study period, if a non-protocol-required visit is done for the purpose of medically-indicated follow-up for either study eye, data from this visit should be submitted using the Unscheduled Visit CRF. The need for unscheduled visits is at the investigator's discretion. Specific examinations to be performed at unscheduled visits are also at the discretion of the investigator (based on the reason for the unscheduled visit), and data are to be recorded in the appropriate section of the case report form.

Data to be collected may include:

- Uncorrected and best corrected distance visual acuity
- Manifest refraction
- Intraocular pressure
- Slit-lamp examination for medical and/or lens findings
- Dilated fundus exam
- Adverse events
- Ocular Medications

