11.3 ADVERSE EVENT AND COMPLAINT REPORTING REQUIREMENTS

All adverse events and any complaint encountered using any JJSV product, regardless of severity and whether or not attributed to the study device(s), are to be reported to JJSV and recorded on the case report form corresponding to the visit during which awareness of the event occurred. Adverse events are also to be reported to the reviewing IRB as per the IRB reporting requirements. If required, adverse events will be reported to the appropriate regulatory agencies (e.g., FDA) according to all applicable laws and regulations.

Reporting of adverse events shall follow the USA Code of Federal Regulations (21CFR812).

General guidelines are provided below:

Adverse Event Reporting

An adverse event that is not serious or device-related is to be reported to JJSV in a timely manner. Notification of non-serious and non-device related adverse events will occur by recording events on the CRF when noted. Such adverse events are also to be reported to the reviewing IRB per their reporting requirements.

Complaints/Device Deficiency Reporting

A general product complaint or device deficiency is to be reported to JJSV in a timely manner. Notification of complaints/device deficiencies will occur by either recording complaints on the CRF when the complaint occurred (e.g. operative form) or by a phone call to the Sponsor. Any device deficiency that could have led to a serious adverse event without suitable action or intervention, or under less fortunate circumstances, must be reported to the sponsor immediately (no later than 24 hours after detection). Device deficiencies that could have led to a serious adverse event should also be reported to the investigator's IRB per their reporting requirements.

Serious and/or Device-Related Adverse Event Reporting

Serious and/or device related events (ADEs) are to be documented using the Detailed Adverse Event CRF. In the event of a serious adverse event (SAE), which may or may not be related to use of the study device, JJSV must be notified immediately (no later than 48 hours after detection). Any SAE is to be reported by phone (and/or email) and by submitting the completed Detailed Adverse Event CRF. Any SAE or device-related AE should also be reported to the investigator's IRB/IEC per their reporting requirements.

Unanticipated Adverse Device Effect (UADE)/Unanticipated Serious Adverse Device Effect (USADE) Reporting

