19. STATISTICAL METHODS

This section highlights the analyses for the primary and other key endpoints. The detailed plan for all analyses will be documented in the Statistical Analysis Plan (SAP). Data from the 3-month postoperative visit will be the key timeframe for the primary and key endpoints. The operative day visit is the key analysis time point for the user acceptance endpoint. Data from other study visits will be reported for supportive analysis. All complications and adverse events will be evaluated at all visits.

Summary statistics include mean, standard deviation, median, minimum, and maximum for continuous variables, and frequency counts and proportions for categorical endpoints. In addition to the point estimates, the appropriate 95% confidence interval may be calculated. All descriptive summaries will be presented by OVD. [REDACTED]

[REDACTED]

[REDACTED]

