19.3 STUDY ENDPOINTS

Primary Endpoints

The safety population will be the primary analysis set for the primary safety endpoint; the mITT population will be the primary analysis set for the primary effectiveness endpoint.

SAFETY: CUMULATIVE RATE OF IOP SPIKES 30 MMHG OR GREATER MEASURED POSTOPERATIVELY

The cumulative count and proportion of eyes with an IOP spike at 3 months will be reported by OVD groups. Cumulative IOP spikes are defined as an IOP of 30 mmHg or greater at any visit.

[figure not shown]
Hypothesis Testing

The null and alternative hypotheses for testing the non-inferiority of the test Healon EndoCoat PRO OVD compared to the control Healon EndoCoat OVD with respect to cumulative IOP spike rate at 3 months (p) are as follows:

$$H_0: p_{test-control} \geq \delta$$
$$H_A: p_{test-control} < \delta$$

Success Criteria: the upper bound of the 2-sided 95% confidence interval for $p_{test-control}$ is less than 10%.

[REDACTED]

EFFECTIVENESS: MEAN PERCENT ECC CHANGE PREOPERATIVELY VS. POSTOPERATIVELY

The percent change in ECC from preoperative to 3 months postoperative will be reported by descriptive statistics by OVD groups. The percent change in ECC from preoperative to postoperative is calculated as followed:

Percent change in ECC = [(Postop ECC minus Preop ECC)/Preop ECC] *100%

Hypothesis Testing

The null and alternative hypotheses for testing the non-inferiority of the test Healon EndoCoat PRO OVD compared to the control Healon EndoCoat OVD with respect to percent change in ECC at 3 months (μ) are as follows:

$$H_0: \mu_{test-control} \leq \delta$$
$$H_A: \mu_{test-control} > \delta$$

[REDACTED]

Success Criteria: the lower bound of the 2-sided 95% confidence interval for $\mu_{test-control}$ is greater than -5%.

SITE HETEROGENEITY AND OTHER COVARIATES

The analysis of site heterogeneity and of the potential impact of other key covariates [REDACTED] on the primary endpoints will be performed using the safety population observed case data for primary safety endpoint and using the mITT population observed case data for primary effectiveness endpoint.

[REDACTED]

[REDACTED]

[REDACTED]

[REDACTED]

Other Endpoints

The Safety population will be used for the analyses of all safety and other endpoints.

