## 2 GENERAL STATISTICS

### 2.1 ANALYSIS POPULATIONS

- mITT: modified ITT population will consist of all randomized subjects who have any investigational or control OVD used. Subjects will be analyzed as per planned randomization schema.
- Safety: Safety Population (SP) will consist of all subjects who have any investigational or control OVD used or attempted use (defined as either OVD system coming into contact with the eye) and analyzed per treatment received.

- Per-Protocol: Per-Protocol Population will include subjects with an investigational or control OVD used, evaluated within the proper study interval and without clinically relevant protocol deviations (deviations that could potentially impact the primary or secondary endpoints) in both eyes as determined prior to database lock.

- [REDACTED]
- [REDACTED]
- [REDACTED]
- [REDACTED]
- [REDACTED]
- [REDACTED]

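### Does the loose sentence on cumulative events in SAP 6.5 change which eyes and visits are counted?

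*SAP*

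**What the plan says.** SAP 6.5 covers medical findings and adverse events that are neither serious nor device-related. Its first sentence plans counts and proportions of eyes over time, by OVD. Its second turns to cumulative complications and adverse events, "occurring at any time postoperative either at standard visits) will include data from all study eyes implanted".

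The surrounding text sets the population and the visits:

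- SAP 6, the parent section: "The safety population will be used for the analyses of all other endpoints".
- SAP 2.1 places in the Safety population all subjects with any investigational or control "OVD used or attempted use (defined as either OVD system coming into contact with the eye"), analysed by treatment received. Lens implantation is not a condition.
- Protocol 19.3, under Other Endpoints: "The Safety population will be used for the analyses of all safety and other endpoints".
- Protocol 19: "All complications and adverse events will be evaluated at all visits".
- Protocol 10.9, on follow-up: "If a subject receives the study or control OVD in at least one eye, he/she is to be followed according to the protocol".

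**The concern.** The study products are viscoelastics, so an *implanted* eye most naturally means one that received an intraocular lens. An eye that was exposed to an OVD but left surgery without a lens belongs to the Safety population, yet falls outside that description. If the lens was withheld because of a complication, the eyes dropped could be the ones with events.

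The visit phrase is also incomplete. It offers one half of a choice and names only standard visits. Protocol 10.10 provides a separate form for unscheduled visits and lists adverse events among the data it may carry. An event recorded only on that form could be missed by someone who programmed from the phrase alone.

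Taken literally, then, two programmers could use different denominators and different source forms for the same safety table. At stake would be a small distortion of descriptive cumulative rates, and a table that does not agree with the population named in its own section heading.

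**Working it through.** The documents state no figure that could be reproduced here. The check is mainly a comparison of texts, with a short calculation for scale.

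**Step 1: population**

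| Place | Eyes or subjects counted |
|---|---|
| SAP 6.5 | study eyes described as implanted |
| SAP 6 | Safety population for all other endpoints |
| Protocol 19.3 | Safety population for safety and other endpoints |
| SAP 2.1 and protocol 19.1 | OVD use, attempted use or contact; no lens condition |
| Protocol 10.9 | follow-up once an OVD is received in at least one eye |

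Four of the five rows agree. The fifth says its data will include certain eyes. It does not say *only*, and it does not set aside the section-level rule. Both can therefore be honoured by using the Safety population.

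The gap between the two sets is also likely to be small. Lens implantation must be planned in both eyes (protocol 8.1). Protocol 10.9 does mention an aborted implant, but among the reasons why a randomized subject had no surgery or received no OVD. It does not clearly describe an exposed eye left without a lens. Such an eye is possible, but the documents give no number.

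**Step 2: visits**

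| Place | Visits covered |
|---|---|
| SAP 6.5 | any postoperative time, then an unfinished phrase naming standard visits |
| Protocol 19 | all visits |
| Protocol 11.3 | every event, "recorded on the case report form corresponding to the visit during which awareness of the event occurred" |
| Protocol 10.10 | unscheduled visits: "data from this visit should be submitted using the Unscheduled Visit CRF" |
| Protocol 10.8 | each visit checks for new events and for changes in known ones |

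The opening words of the SAP parenthesis already span the whole postoperative period, and the protocol rule covers every visit. Events found between scheduled visits reach the database through protocol 11.3 and 10.10. Many would also surface at the next scheduled visit, because protocol 10.8 asks about change in status. The literal reading would lose only events that appear on an unscheduled form and nowhere else.

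**Step 3: scale per eye, for illustration**

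Inputs: protocol 10.1 gives up to 195 enrolled subjects and about 114 treated in both eyes and evaluable at 3 months. With one eye per OVD per subject, take N = 114 and N = 195. These are reference values and not true bounds: some subjects may receive an OVD in one eye only, 114 is a target for evaluable subjects, and 195 caps enrolment. Event rates of 5% and 20% are assumptions; n is the resulting number of eyes with events.

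- Event not counted, denominator unchanged, 1/N: 1/114 = 0.88 points; 1/195 = 0.51 points.
- Exposed eye with an event left out, fall = n/N − (n−1)/(N−1):
  - N = 114: 6/114 − 5/113 = 0.84 points; 23/114 − 22/113 = 0.71 points.
  - N = 195: 10/195 − 9/194 = 0.49 points; 39/195 − 38/194 = 0.41 points.
- Event-free eye left out, rise = n/(N−1) − n/N:
  - N = 114: 6/113 − 6/114 = 0.05 points; 23/113 − 23/114 = 0.18 points.
  - N = 195: 10/194 − 10/195 = 0.03 points; 39/194 − 39/195 = 0.10 points.

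Dropping an eye can therefore move the rate either way, and each eye moves it by less than one percentage point.

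**Step 4: what depends on the sentence**

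The two primary endpoints are defined in SAP 5.1 and 5.2 with their own populations. The comparison of adverse-event rates with ISO reference rates is in SAP 6.4. None of these refers to the sentence in 6.5.

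**The case for a change.** The best argument for a change is that the specific text usually guides the programmer. SAP 6.5 names its own set of eyes, so someone working from that subsection could follow it in good faith and never return to the sentence at the head of section 6. The tables concern safety, and an eye left without a lens after a complication is one that should not drop out. An edit would take one sentence and no new data.

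Part of this stands. The sentence is badly worded: *implanted* is not the defined term, and *either* lacks its partner. Anyone revising the SAP for another reason could tidy it.

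The step from there to a required change does not stand. For the narrow reading to take effect, an analyst would have to treat a statement of inclusion as an exclusion, against the section's own population rule and against two statements in the protocol. Nor is it shown that programmers would differ. The SAP change history says that Appendix I, the table listing, carries analysis populations for some tables, and that appendix is not in the text available here. A rewrite also carries a risk of its own: SAP 2.3 counts preoperative and operative visits among the study visits, so wording that covers all visits without keeping the postoperative limit would widen the scope of the table.

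**Conclusion.** The sentence is a clerical slip, and no change to the plan follows. The section-level population rule and the protocol's visit rule already give the correct table: Safety population eyes by OVD received, with postoperative events from scheduled and unscheduled visits alike. A competent analyst would build it that way.

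The total effect of the narrow reading cannot be quantified from the documents. Under the illustrative counts above, each affected eye would shift a descriptive rate by at most 0.88 points. The conclusion rests on two things: that the section 6 rule governs its subsections, and that the 6.5 tables stay descriptive. The documents support both. No hypothesis test, success criterion or primary endpoint depends on the sentence.
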